5.5 Safety Analysis

All safety analyses will be conducted based on SS. All safety analyses will be presented by treatment group.

5.5.1 Extent of exposure

See Section 5.1.3 for the specific defining rules of the derived variables of study drugs SHR-1210, apatinib, doxorubicin, and ifosfamide.

The drug exposure, duration of drug exposure, actual dose intensity, and relative dose intensity of apatinib and SHR-1210, as well as the duration of drug exposure and drug exposure of doxorubicin and ifosfamide are described using the mean, standard deviation, maximum, minimum, and median.

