5.1.3 Derived variables

Table 1. Derived variables of SHR-1210

Variable	SHR-1210
Protocol-Specified Method of Administration	200 mg/dose, intravenous drip (no less than 20 min and no more than 60 min) on Day 1 of each 3-week cycle.
Duration of Drug Exposure (Month)	(Actual date of last dose – actual date of first dose + 21)/30.4375
Drug Exposure (mg)	The total administered dose of SHR-1210 in the subject
Actual Dose Intensity (mg/3 weeks)	Drug exposure/[duration of drug exposure (month) \times 30.4375/21]
Relative Dose Intensity (%)	100 \times actual dose intensity (mg/3 weeks)/200 (mg/3 weeks)

Table 2. Derived variables of apatinib

Variable	Apatinib
Protocol-Specified Method of Administration	Administered orally at 500 mg/day once daily. Each cycle contains 3 weeks.
Duration of Drug Exposure (Month)	(Actual date of last dose – actual date of first dose + 1)/30.4375
Drug Exposure (mg)	The total administered dose of apatinib in the subject
Intended Dose Intensity (mg/day)	500
Actual Dose Intensity (mg/day)	Drug exposure (mg)/[duration of drug exposure (month) \times 30.4375]
Relative Dose Intensity (%)	100 \times actual dose intensity (mg/day)/500

Table 3. Derived variables of doxorubicin

Variable	Doxorubicin
Protocol-Specified Method of Administration	Administered via intravenous drip infusion at 60 mg/m ² within 2 h on Day 1 of each 3-week cycle.
Duration of Drug Exposure (Month)	(Actual date of last dose – actual date of first dose + 21)/30.4375
Drug Exposure (mg/m ²)	Subject's actual cumulative dose (mg)/body surface area ⁽¹⁾
Intended Dose (mg/m ²)	(Actual date of last dose – actual date of first dose + 21) \times 60 mg/m ² /21
Relative Dose Intensity (%)	100 \times drug exposure (mg/m ²)/scheduled dose (mg/m ²)

Table 4. Derived variables of ifosfamide

Variable	Ifosfamide	
Protocol-Specified Method of Administration	Combination with doxorubicin: Ifosfamide 2 g/m ² /d on D1-D4, intravenous drip infusion within 4-6 h, in 3-week cycles (i.e., the total dose per cycle shall be 8 g/m ²).	Ifosfamide monotherapy: 2 g/m ² /d on D1-D5, intravenous drip infusion within 4-6 h, in 3-week cycles (i.e., the total dose per cycle shall be 10 g/m ²).
Duration of Drug Exposure (Month)	(Actual date of last dose – actual date of first dose + 21)/30.4375	
Drug Exposure (g/m ²)	Actual cumulative dose/body surface area ⁽¹⁾	

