Intended Dose (g/m ²)	[(Date of last dose of doxorubicin – date of first dose of doxorubicin + 21)/21] × 8 g/m ² + [CEIL × (date of last dose of ifosfamide – date of last dose of doxorubicin – 4)/21] × 10 g/m ²	
Relative Dose Intensity (%)	100 × drug exposure (g/m ²)/intended dose (g/m ²)	

(1) The body surface area is calculated as: body surface area (m²) = 0.0061 × height (cm) + 0.0128 × weight (kg) – 0.1529. The body weight at baseline should be used.

*CEIL: round up

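### Relative dose intensity is derived for the control drugs but not listed for reporting, and ifosfamide exposure duration is overstated by a fixed 3 to 4 days

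*SAP*

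**What the plan says.** SAP 5.1.3 has one derivation table per drug, and each has a row for "Relative Dose Intensity". Table 3 defines it for doxorubicin as 100 times "drug exposure (mg/m ²)/scheduled dose (mg/m ²"). Table 4 defines it for ifosfamide as 100 times "drug exposure (g/m ²)/intended dose (g/m ²").

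SAP 5.5.1 then names what will be summarised. For the investigational drugs it includes "actual dose intensity, and relative dose intensity of apatinib and SHR-1210", along with exposure and duration. For the control drugs it names only "as well as the duration of drug exposure and drug exposure of doxorubicin and ifosfamide". The section refers to 5.1.3 for defining rules, but that reference does not add outputs to the list.

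For duration in months, Tables 1, 3 and 4 use the same expression (opening bracket omitted): "Actual date of last dose – actual date of first dose + 21)/30.4375". SHR-1210 and doxorubicin are given on day 1 only. Ifosfamide is not. In combination, Table 4 has "Ifosfamide 2 g/m ² /d on D1-D4, intravenous drip infusion within 4-6 h, in 3-week cycles"; as monotherapy, "2 g/m ² /d on D1-D5, intravenous drip infusion within 4-6 h, in 3-week cycles".

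**The concern.** The trial is open-label, with IRC-assessed PFS as the primary endpoint and chemotherapy as comparator. Protocol 10.1.6.4 allows chemotherapy to be delayed by up to 6 weeks and reduced once, to 85% of the initial dose, so delivery of the control regimen can vary considerably. Anyone interpreting a PFS difference will ask whether the control regimen was given as intended. The listed outputs answer that directly for the new regimen and only indirectly for the control.

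The duration rule adds a smaller problem. Adding 21 days to a day-1 dose closes the last cycle. Adding 21 days to a D4 or D5 dose runs past its end. The exposure table would then show two different durations for doxorubicin and ifosfamide given in the same cycles.

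**Working it through.** **Inputs.** Cycle length is 21 days (Protocol 11.2.2). Doxorubicin is 60 mg/m² on D1. Ifosfamide is 2 g/m²/d on D1-D4, or D1-D5 as monotherapy. The formulas are those of SAP Tables 3 and 4. Unless a delay is stated, dosing is on schedule, so cycle k starts 21(k − 1) days after the first dose.

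**The plan's own figures.** 2 × 4 = 8 g/m² and 2 × 5 = 10 g/m² per cycle, as Table 4 states.

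**Ifosfamide duration.** Over k cycles the correct count is 21k days. Table 4 gives 21(k − 1) + 3 + 21 = 21k + 3 days in combination, or 21k + 4 if the last cycle is monotherapy. Table 3 gives exactly 21k for doxorubicin.

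| Cycles | Correct, and doxorubicin | Ifosfamide, last cycle combination | Ifosfamide, all monotherapy |
|---|---|---|---|
| 1 | 21 | 24 (+14.3%) | 25 (+19.0%) |
| 2 | 42 | 45 (+7.1%) | 46 (+9.5%) |
| 6 | 126 | 129 (+2.4%) | 130 (+3.2%) |

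The excess occurs once per subject, not once per cycle. At six combination cycles it is 129/30.4375 = 4.24 months against 126/30.4375 = 4.14.

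**Does this enter ifosfamide RDI?** No. Table 4 builds the intended dose from doxorubicin dates, plus a monotherapy term that subtracts 4 days.
- Six combination cycles: (105 + 21)/21 × 8 + CEIL((3 − 4)/21) × 10 = 48 + 0 = 48 g/m². This equals the planned 6 × 8, so RDI is 100%.
- Six combination plus two monotherapy cycles: the last doxorubicin dose is at day 105 and the last ifosfamide dose at 105 + 42 + 4 = 151. Then 48 + CEIL((151 − 105 − 4)/21) × 10 = 48 + 20 = 68 g/m², which equals 6 × 8 + 2 × 10.

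The subtraction of 4 also shows that Table 4 takes the last ifosfamide date as the actual D4 or D5 day.

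**Back-calculation from the reported items.** For six full-dose combination cycles, 48/(8 × 129/21) = 97.7% instead of 100%. For one cycle, 8/(8 × 24/21) = 87.5%. For six cycles at 85% dose, 0.85 × 48/(8 × 129/21) = 83.0% instead of 85%.

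**What the unreported doxorubicin RDI could show.** Table 3's intended dose is (last − first + 21) × 60/21.
- Six cycles, each delayed by 1 week: 5 × 28 + 21 = 161 days; intended 460 mg/m²; given 360; RDI 360/460 = 78%.
- Six cycles at 51 mg/m², each delayed by 2 weeks: 5 × 35 + 21 = 196 days; intended 560; given 306; RDI 306/560 = 55%.

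**Why group summaries are only approximate.** Take one subject with six on-schedule cycles (360 mg/m², 126 days, RDI 100%) and one with two cycles a week late (120 mg/m², 28 + 21 = 49 days, intended 140, RDI 86%). Mean RDI is 93%. Mean exposure over mean duration gives 480/(175 × 60/21) = 480/500 = 96%. That ratio weights subjects by time on drug, so a subject who stops early after poor delivery counts least.

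**The case against.** The strongest reply is that this is a descriptive gap with little practical effect, and much of that reply stands.

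A reader might infer that under-delivery of the control regimen cannot be judged at all. The documents do not support that. SAP 5.5.1 summarises both exposure per m² and duration for each control drug. For a single subject on doxorubicin, exposure over duration is RDI up to a constant. The 1-week-delay example would show as 360 mg/m² over 161 days (5.29 months) against 126 days (4.14 months) on schedule, so it would be visible. SAP 5.5.2 also summarises AEs leading to dose reduction, interruption or discontinuation, and SAP 5.5 presents safety analyses by treatment group.

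A reader might also infer that the duration error hides under-delivery or distorts ifosfamide RDI. It does neither. RDI does not use the duration row, and a longer denominator makes back-calculated delivery look worse.

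Finally, simple per-cycle arithmetic (21/28 = 75% and 0.85 × 21/35 = 51%) overstates the shortfall the SAP would record, because Table 3 credits the last cycle with only 21 days. The six-cycle figures are 78% and 55%.

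What the reply does not remove is the lack of a like-for-like measure. A ratio of means gives neither the mean nor the spread of subject-level RDI. For ifosfamide it is rougher still, because cycles of 8 and 10 g/m² are mixed. The AE summaries count subjects but give no size or length of change, and they miss delays not attributed to an AE.

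**Conclusion.** The point holds as a minor reporting defect in two separate parts.

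First, RDI is derived for all four drugs and listed for two, so the arms are not compared on the same delivery measure and control delivery can be read only approximately.

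Second, ifosfamide duration is too long by 3 days per subject, or 4 if the last cycle is monotherapy. That is about 0.1 month and 2.4% over six combination cycles; the 14% to 19% excess applies only to subjects with a single cycle. It contradicts the doxorubicin duration for the same cycles.

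Neither part affects the primary test, alpha, power or any efficacy estimate. No data are lost, and RDI could be tabulated later from the same records.

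Assumptions: on-schedule dosing for the duration figures; the last-dose date read literally as D4 or D5; CEIL read as the round-up function its footnote describes, although it is printed with a multiplication sign; and Table 3's scheduled dose taken to be its intended-dose row. The 55% example assumes the reduced dose from the first cycle. With 60 mg/m² in cycle 1 and 51 after that, it is (60 + 5 × 51)/560 = 315/560 = 56%.

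**What to change.** - In SAP 5.5.1, add relative dose intensity of doxorubicin and ifosfamide to the summarised variables, with the same statistics as for the investigational drugs.
- In Table 4, calculate ifosfamide duration as (day 1 of last cycle − day 1 of first cycle + 21)/30.4375. On-schedule dosing then gives 21 days for one cycle and 126 for six, matching doxorubicin.
- In Table 4, state how intended dose is calculated for a subject who receives ifosfamide without doxorubicin. The present formula needs doxorubicin dates, yet Protocol 10.1.5 sends subjects with too little remaining anthracycline allowance straight to ifosfamide monotherapy.

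The cost is small: a few lines of SAP text and matching programming, with no new data collection. The SAP describes itself as an initial version to be finalised before database lock, so the change can be made in the normal course. Counts of cycles and of delays not due to AEs would be useful, but they need definitions that 5.1.3 does not yet contain and are optional.

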5.5.2 Adverse event

AEs will be classified by treatment stage (before and after study treatment).

All AEs will be coded with MedDRA (version, 23.1). and graded using NCI-CTCAE v4.03. For the same SOC and/or PT, multiple cases of the same events that occur in one subject will be counted only once. For the same AE reported in one subject multiple times but varying in CTCAE grade, the AE of the greatest grade will be enumerated.

AEs will be sorted by incidence from high to low based on SOC, and PT under each SOC. If the incidence of ≥ 2 PT is equal, the AEs will be sorted alphabetically. If there is no AE under a SOC or PT, then analysis will not be conducted.

A treatment-emergent adverse event (TEAE) is defined as any adverse event that occurs after the start of study treatment. Only TEAEs will be summarized. All AEs will be listed. AEs with completely missing onset time will be treated as TEAEs.

For AEs occurring after the start of study treatment, treatment-related AEs include those whose causality with the study drug is definitely related, possibly related, or indeterminable; if the causality assessment is missing, then the AE will be deemed treatment-related for analysis.

In a listing of AEs, TEAEs will be analyzed by group, and frequencies and proportions will be statistically described. AEs will be summarized using descriptive statistics according to Hengrui's Statistical Analysis Reporting Standards, including but not limited to the following contents:

- Any TEAE
- Treatment-related AEs (TRAEs)
- Any TESAE
- Treatment-related SAEs (TRSAEs)
- Any SAE
- Any drug-related SAE
- TEAEs resulting in dose reduction, dose interruption followed by reduction, interruption, or treatment discontinuation
- TRAEs resulting in dose reduction, dose interruption followed by reduction, interruption, or treatment discontinuation
- TEAEs resulting in death
- Immune-related adverse events ("reactive capillary endothelial proliferation" will all be considered immune-related events)?
- Was hormone therapy used?

The incidence of AE is calculated based on the number of subjects having an AE, instead of the number of AE episodes.

All AEs will be listed. Drug-related AEs, AEs resulting in treatment discontinuation, AEs resulting in dose reduction or dose interruption followed by reduction or treatment interruption, and death will be listed.

5.5.3 Laboratory tests

Baseline laboratory measurement is defined as the latest non-missing test result prior to the first dose of study drugs.

Laboratory results will be listed.

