Data Analysis/ Statistical Methods	
This study plans to conduct an interim analysis for efficacy and a final analysis. The interim analysis will be carried out when 67% of PFS events (approximately 143 subjects) are collected to determine whether the drug is effective and whether to terminate or continue the study. The final analysis will be performed when the number of PFS events reaches 214.
 
 ■ General analysis 
For this study, efficacy data will be summarized in accordance with the following general principles using descriptive statistics, unless otherwise stated.

	
Two-category and multi-category data will be summarized using frequency and percentage.
 
Measurement data will be summarized using mean, standard deviation, median, maximum, and minimum.
 
Time-event data will be analyzed using the Kaplan-Meier method, so as to estimate the survival function of both groups and plot the survival curves.
 
All statistical analyses will be performed using SAS version 9.4 or later.
 
 ■ Efficacy analysis 
In addition to the general principles of efficacy analysis described above, the analysis of primary and secondary efficacy indicators also includes:
 
ORR and DCR: The Clopper-Pearson method will be used to calculate the 95% confidence interval of the ORR.
 
PFS and OS: The Kaplan-Meier method will be used to plot the survival curve, and the Brookmeyer Crowley method will be used to calculate the 95% confidence interval of the median survival. In addition, the Cox regression model will be used to estimate the hazard ratio between the two groups and its 95% confidence interval (95% CI).
 
The general analysis principle also applies to DoR analysis, but whenever necessary, the 95% confidence interval of the median survival will be calculated to estimate and plot the survival curve.
 
 ■ Safety analysis 
The AEs, SAEs, and adverse drug reactions will be analyzed mainly using descriptive statistics. Laboratory tests that are normal before the study but become abnormal after starting treatment will be described.

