6.1.2 Secondary objectives

- To evaluate and compare the overall survival (OS), objective response rate (ORR), duration of response (DoR), and disease control rate (DCR) in subjects with soft tissue sarcoma after treatment with SHR-1210 combined with apatinib vs. doxorubicin combined with ifosfamide;
- To evaluate and compare the safety of SHR-1210 combined with apatinib vs. doxorubicin combined with ifosfamide in the treatment of soft tissue sarcoma;
- To evaluate and compare the quality of life scores in subjects with soft tissue sarcoma after treatment with SHR-1210 combined with apatinib vs. doxorubicin combined with ifosfamide.

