6.2.2 Secondary endpoints

- PFS assessed by the investigator (as per RECIST v1.1)
- OS
- ORR assessed by the investigator and independent review committee (as per RECIST v1.1)
- DoR assessed by the investigator and independent review committee (as per RECIST v1.1)
- DCR assessed by the investigator and independent review committee (as per RECIST v1.1)
- Incidence and severity of AEs and SAEs, vital signs, ECG, and laboratory abnormalities.
- Quality of life score (EORTC QLQ-C30)

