14.4.5 Safety analysis

AEs that occur during the study will be coded according to MedDRA. The frequency and incidence of AEs will be summarized by system organ class and preferred term. The relevance and severity of AEs will be further tabulated for description. Descriptive statistics will be used to summarize other safety endpoints. Summarize the incidence of AEs, adverse drug reactions, AEs resulting in withdrawal from the study, AEs resulting in death, and SAEs. Severity of adverse events and adverse drug reactions: For the same AE with multiple occurrences in the same subject, the highest severity will be included in the analysis; for different AEs occurring in the same subject, the most severe AE will be included in the analysis.

Laboratory tests: Abnormal laboratory values will be summarized using descriptive statistics.

Vital signs: Measured values and changes will be summarized using mean, maximum, minimum, median, and SD.

Physical examination and 12-Lead ECG will be summarized descriptively.

Baseline is defined as the most recent test data before the first dose.

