5.5.4 Vital signs

All vital signs will be listed.

5.5.5 12-Lead ECG

Mean values of 12-Lead ECG results will be taken at each visit. ECG data include: HR (beats/min), PR interval (ms), QT interval (ms), and QTcF (ms).

ECG parameters measured at the study site will be summarized as follows:

- Maximum PR interval \geq 300 ms
- Maximum QT interval \geq 500 ms
- Maximum QTcF interval (ms) (450–<480, 480–<500, or \geq 500)
- Maximum QTcF interval \geq 480 ms or increase $>$ 60 ms from baseline

Related data will also be listed.

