5.5.8 Other safety measures

Echocardiography will be listed by treatment group and time.

Pregnancy test results will be listed by treatment group and time.

Observation results of reactive capillary endothelial proliferation will be listed.

The subjects' virological examinations will be listed.

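### SAP 5.5.3 and 5.5.4 reduce laboratory tests and vital signs to listings, although SAP 4.2 and Protocol 14.4.5 call for summaries of this part of the secondary safety endpoint

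*SAP*

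**What the plan says.** The protocol sets a secondary objective "To evaluate and compare the safety of SHR-1210 combined with apatinib vs. doxorubicin combined with ifosfamide in the treatment of soft tissue sarcoma" (Protocol 6.1.2) and, among the secondary endpoints, "Incidence and severity of AEs and SAEs, vital signs, ECG, and laboratory abnormalities" (Protocol 6.2.2). It then says how two of these elements will be reported:

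- Laboratory tests: "Abnormal laboratory values will be summarized using descriptive statistics" (Protocol 14.4.5). The synopsis adds: "Laboratory tests that are normal before the study but become abnormal after starting treatment will be described".
- Vital signs: "Measured values and changes will be summarized using mean, maximum, minimum, median, and SD" (Protocol 14.4.5).

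SAP section 1 states that the SAP was drafted from protocol version 3.0. SAP 4.2 names laboratory and vital-signs data among the safety data to be summarised as the protocol provides. The analysis sections say something else. SAP 5.5.3 defines a laboratory baseline and then says "Laboratory results will be listed". SAP 5.5.4 says "All vital signs will be listed" and nothing more. SAP 5.5.5, by contrast, gives categorical summaries of PR, QT and QTcF and also lists the ECG data. SAP 5.5.8 says "Echocardiography will be listed by treatment group and time".

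**The concern.** A listing shows one subject's values after another. It gives no count of subjects with an abnormality, no severity distribution and no change from baseline by arm. If programming follows SAP 5.5.3 and 5.5.4, the laboratory and vital-sign elements of the endpoint have no result, although the protocol promised one and the SAP gives no reason for dropping it.

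This matters more than usual because the trial is open-label. A laboratory change enters the adverse event tables only if it is judged clinically significant or a worsening of a pre-existing condition (Protocol 13.1.1, SAP 4.2.1), and the person judging knows the treatment. Summaries of measured values are the natural check on that judgement.

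**Working it through.** No figure has to be reproduced here; the check is a comparison of texts, followed by a count of scheduled assessments to see what a fair table can contain.

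**Step 1. Plan against implementation**

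| Element of the endpoint | Protocol 14.4.5 and synopsis | SAP 4.2 | SAP analysis section |
|---|---|---|---|
| Adverse events | Incidence and severity | Summarised | By-group tables, CTCAE-graded (5.5.2) |
| ECG | Descriptive summary | Summarised | Categories and listing (5.5.5) |
| Laboratory tests | Abnormal values; normal-to-abnormal changes | Summarised | Listing only (5.5.3) |
| Vital signs | Values and changes | Summarised | Listing only (5.5.4) |

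Two of four elements lack an implementing analysis.

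**Step 2. Does a general SAP rule fill the gap?** The default descriptive statistics in SAP 5.1.2 yield wherever something else is specified, and 5.5.3 and 5.5.4 do specify something: a listing. SAP 5.5 says safety analyses are shown by treatment group, which turns a listing into a listing by arm, not a summary. The ECG section, next in order, orders both summaries and a listing, so the SAP does distinguish the two. SAP 5.1.2 also sets rules for values recorded as below or above a limit, and 5.5.3 defines a baseline, but no specified laboratory analysis uses either.

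**Step 3. What can be tabulated fairly?** Scheduled assessments on day 1 of cycles 2 to 6, from the schedules in Protocol sections 1 and 2 and from Protocol 11.2:

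| Test | Control | Investigational |
|---|---|---|
| Haematology, biochemistry, vital signs | 5 (C2 to C6) | 5 (C2 to C6) |
| Urinalysis, coagulation | 5 (C2 to C6) | 2 (C3, C5) |
| Thyroid function | 0 | 2 (C3, C5) by the schedule table and 11.2.1; 5 by footnote 12 of section 1 |
| Echocardiography | 5 (C2 to C6) | 0 |

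After the last dose, the control arm has a visit at 21 days that includes thyroid function and echocardiography (Protocol 11.3.2). The investigational arm has a visit at 30 days that includes thyroid function but not echocardiography (Protocol 11.3.1). Treatment length also differs: six 3-week cycles are recommended in the control arm (6 × 3 = 18 weeks, with more allowed), against up to 2 years of SHR-1210.

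Three consequences follow. Haematology, biochemistry and vital signs can be compared visit by visit through cycle 6. For urinalysis, coagulation and thyroid function, a worst-value table rises with the number of tests, so it needs the number of assessments and exposure beside it. For thyroid function, the 21-day visit is the control arm's only scheduled post-baseline result, so a strict on-treatment window would delete it.

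**The case against.** The strongest reply is that the SAP never abandoned the summaries. SAP 4.2 promises them, Protocol 14.4.5 defines them, and SAP 5.1.2 supplies default statistics and a rule for censored laboratory values that a pure listing would not need. What stands is that the SAP contradicts itself rather than openly dropping an analysis, and the summary text may simply have been left out. But the sections that direct the output order only listings, and the defaults give way to them.

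A second reply is that laboratory toxicity reaches the by-group adverse event tables. This is largely true. Protocol 13.1.3 asks that changes in objective laboratory measurements be recorded, and the background rates in Protocol 5.3 (AST increased 21.7%, anaemia 27.5%, proteinuria 22.1%) are themselves treatment-related adverse event rates. They show such toxicity being captured as adverse events, so they cannot be used as a measure of what the SAP loses. What remains is the dependence on an unblinded investigator's judgement.

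A reader might also infer three stronger points that the documents do not support:

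- That objective safety measures are never compared between arms. ECG is objective, belongs to the same endpoint and is summarised.
- That a by-arm LVEF comparison has been lost. LVEF is not named in the endpoint, and the investigational arm has echocardiography at baseline and afterwards only if clinically indicated (Protocol 11.1). A by-arm table of lowest LVEF would be an artefact of the schedule.
- That a formal safety test has been dropped. Protocol 14.4.5 plans descriptive summaries only.

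**Conclusion.** The point holds in limited form. SAP 5.5.3 and 5.5.4 conflict with SAP 4.2, Protocol 14.4.5 and the synopsis. Followed literally, they leave laboratory tests and vital signs without any by-arm incidence or change from measured values. The loss is descriptive and confined to the secondary safety objective; the PFS analysis, its error rate and the sample size are untouched.

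The conclusion assumes that 5.5.3 and 5.5.4 govern the output. SAP 5.5.2 refers to the sponsor's reporting standards, but for adverse events only. If table specifications outside these documents already contain the missing summaries, only the contradiction in wording remains. It is worth correcting either way, since SAP section 1 provides for finalisation before database lock.

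**What to change.** Amend SAP 5.5.3 and 5.5.4, keep the listings, and add by-arm descriptive tables on the safety set, using control-arm data up to the first crossover dose:

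1. Laboratory tests: number and percentage with abnormal values, and shift from baseline, for example worst post-baseline CTCAE v4.03 grade derived from the measured values. This covers both the abnormal-value summary and the normal-to-abnormal description.
2. Vital signs: values and changes from baseline by visit, with the statistics already named in Protocol 14.4.5.
3. Comparability: show results at common visits, or give the number of assessments and exposure per arm, especially for thyroid function, urinalysis and coagulation. Define the window so that it keeps the control arm's 21-day visit. Reconcile the investigational arm's thyroid schedule (each cycle or every two cycles) so that the denominators are clear.
4. LVEF: no between-arm table; at most a descriptive summary in the control arm.

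If the sponsor prefers listings only, the SAP should say why Protocol 14.4.5 is not followed and bring SAP 4.2 into line. The cost is some SAP wording and a few standard tables from data already collected.
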